9.1. Schedule of Events

For patients who meet all of the inclusion criteria and none of the exclusion criteria, step-wise endoscopic RFA will be performed in 3month intervals \pm 4 weeks from the first RFA per the Patient Flow Diagram (Figure 1). Each decision point in the flow diagram regarding endoscopy, staining, RFA, biopsy, and patient advancement to subsequent study visits is fully delineated in the diagram. The study primary endpoint biopsies are obtained at 12 months from the initial treatment.

Study procedures are summarized in Table 2 and described in detail below.

Table 2. Study Schedule and Assignments

	BQE (1 week to 3 months before first RFA)	Baseline assessmen ts	Primary RFA	3-Month Follow-Up visit (from primary RFA, \pm 4 weeks)	6-Month Follow-Up Visit (from primary RFA, \pm 4 weeks)	9-Month Follow-Up Visit (from primary RFA, \pm 4 weeks)	12-Month- Primary Endpoint (from primary RFA, \pm 4 weeks)	2-3-4-5 Year Follow-up (from primary RFA, \pm 4 weeks)
	BQE is part of regular care		After insertion of RFA catheter, patient is considered enrolled in the study: treatment phase					Follow-up phase
Informed Consent		X						
Patient History CRF		X						
Baseline Qualifying CRF		X						
Confirmation of Study Eligibility CRF		X						
Upper Endoscopy using Lugol's Solution	X			X	X	X	X	X
Circumferential RFA at 12 J/cm ²			X					
Endoscopy CRF			X	X	X	X	X	X
Table of findings CRF			X	X	X	X	X	X

Medtronic Confidential

COVB3050540 (REACH) Clinical Investigation Plan

Version 7.0

15-Mar-2018

Page 26 of 62

	BQE (1 week to 3 months before first RFA)	Baseline assessmen ts	Primary RFA	3-Month Follow-Up visit (from primary RFA, +/- 4 weeks)	6-Month Follow-Up Visit (from primary RFA, +/- 4 weeks)	9-Month Follow-Up Visit (from primary RFA, +/- 4 weeks)	12-Month- Primary Endpoint (from primary RFA, +/- 4 weeks)	2-3-4-5 Year Follow-up (from primary RFA, +/- 4 weeks)
Circumferential or focal RFA at 12 J/cm ²				X	X	X		X
Biopsy	X			X	X ¹	X ¹	X	X
Central pathology review (BQE biopsy)		X						
Central pathology review				X	X	X	X	X
2 nd pathologist assessment		X					X	X ²
Pathology CRF		X		X	X	X	X	X
Study Exit CRF								X ⁴
Safety Assessment			X	X	X	X	X	X
Observation of endoscopy by CICAMS expert			X	X	X	X	X	X
Keyhole biopsy if diagnosis of suspicious/visible lesion needed before escape treatment				X	X	X	X	X
Escape treatment (see section 9.4.3) for ESCC/ disease suspicious for ESCC				X	X	X		X

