Escape treatment if residual ESCN							X	X ³

Remarks:

¹ Biopsies at 6 and 9 months will be performed only if USL are detected after CR

Medtronic Confidential

² Only recurrent or progressive disease during FU will be assessed by a second expert pathologist. This includes biopsies indicating recurrent or progressive disease, and eventual EMR/ESD/surgery specimens.

³ If persistent after 4 additional RFA sessions

⁴ Study completion is defined as when all follow-up visits have been completed, all data has been entered, reviewed, monitored, and database has been locked.

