If an indication for additional RFA exists, the investigator will determine whether to provide secondary RFA with the circumferential or focal device, based on the extent of disease:

- If lesions involve more than 3/4 of the circumference, circumferential RFA will be used
- If lesions involve less than 3/4 of the circumference, focal RFA will be used
 - It is presumed that all secondary RFA procedures will be performed with the focal device, and this presumption is reflected in Figure 1.

If focal RFA is selected, it is important to note that the effect of Lugol's may significantly wane during the biopsy procedures therefore it may be necessary to reapply the Lugol's in order to target the remaining USLs. Or simply use the biopsy sites for targeting. Each USL is treated so that the ablation effect overlaps at least 5 mm onto the normal staining esophageal mucosa surrounding the USL. The energy density setting is 12 J/cm² and the power density setting is 40 W/cm². Each USL is ablated 3x without changing the position of the catheter. Upon completing focal RFA of USL(s), biopsies are obtained from the TA avoiding all acute RFA sites. Two biopsy fragments are obtained from every 2 cm of the original USL-bearing esophagus that was not treated at this session (see Figure 1).

Example: TA from 30-40, USL bearing esophagus 31-39. One USL at 3 months from 31-32. Sample USL, then RFA USL. Then obtain 2 biopsy fragments from every 2 cm starting at 33-35, 35-37, and 37-39 cm. The area of the USL is avoided (31-33 cm).

In the unlikely event that circumferential RFA is selected for a follow-up RFA, the entire extent of original TA is treated, using same technique as at the primary RFA session.

If necessary, a maximum of four RFA sessions will be performed in total for each patient in this study. If USLs with MGIN or worse in the TA persist after four sessions, the subject is considered a failure for the primary endpoint. Such patients will undergo escape treatment.

Scenario #3: Lesions Suspicious for ESCC Are Present in the TA

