If any **non-flat USL (Paris type 0-I, 0-IIa, 0-IIc, 0-III)** is detected, independent of its staining characteristics upon Lugol's staining, or WLE, NBI or Lugol's chromoendoscopy show a lesion suspicious for ESCC (e.g. 'pink sign' USL, defined as a color change after Lugol's staining: initially whitish yellow and pink 2-3 minutes later), or if previous biopsies from this lesion showed ESCC, subject will be managed with escape treatment (see section 9.4.3 for description), at the discretion of the physician under hospital standard of care depending on the lesion type. If histology is needed before

escape treatment, a keyhole biopsy should be performed, but the Investigator can perform escape treatment if deemed necessary, regardless of the biopsy result. The patient will be considered a failure for the primary efficacy endpoint only if escape treatment histology shows progression to ESCC. If histology does not show ESCC, the patient will return in 3 months from escape treatment for possible RFA and will be eligible for success in the primary endpoint. For continuation on trial, please refer to section 9.4.3.

Scenario #4: USLs are present outside the TA

If any **new USL(s) is (are) detected outside the TA** during follow-up prior to 12 months, it is biopsied and the biopsy fragments are placed in a separate container and labeled as to their location. This finding does not alter the plan for RFA inside TA for that particular procedure, and the USL outside the TA is treated according the standard practice under hospital standard of care.

During all endoscopies, re-tattoos will be performed if necessary. If clinically indicated, extra endoscopies can always be performed.

12 Months Follow-up Endoscopy

No RFA is provided to any subject at the 12-month primary endpoint biopsy visit.

For the biopsy methodology for the primary endpoint:

1. If there are no USLs within the TA, see Section 10.4, "Scenario #1: No USLs are present"
2. If there are one or more persistent USLs within the TA, see Section 10.4, "Scenario #2: USLs are present"

If there are any USLs discovered outside the original USL bearing esophagus, these may be biopsied or resected, but must be submitted in separate containers are not considered in the primary endpoint analysis.

Patients with a CR at 12 months will enter the follow-up phase as described in figure 2 and section 9.4.2.

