9.4.2. Follow-up Phase

All subjects with a CR at 12 months will immediately enter follow-up phase. All patients with residual ESCN at 12 months who achieve CR upon endoscopic escape treatment will also enter the follow-up phase. All patients who progress to ESCC and require escape treatment during the trial, including non-endoscopic, will enter the follow-up phase regardless of primary endpoint failure to assess secondary endpoints. All endoscopies in the follow-up phase will be observed by an expert from CICAMS.

Follow-up procedures include (fig 2):

Annual follow-up endoscopy visit:

- upper endoscopy
- re-tattoo the TA, as necessary
- stain the esophagus with Lugol's solution
- map the entire esophagus for USLs

For TA:

- i. If no USLs in TA, perform biopsies of TA (2 biopsy specimens are obtained for every 2cm segment of the original USL-bearing esophageal segment)
- ii. If unstained lesion (USLs) are found in the TA, each lesion will be biopsied (as described in section 9.4.1, scenario #2). In addition, 2 biopsy specimens are obtained for every 2cm segment of the original USL-bearing esophageal segment that does not now contain USLs. All flat USLs will be treated with RFA. One exception needs to be addressed in line with the treatment phase: clearly reactive USLs may be biopsied and left untreated.
- iii. Any non-flat lesion or lesion suspicious for ESCC (e.g. 'pink sign') in TA will be treated with escape treatment (see section 9.4.3 for description), at the discretion of the physician under hospital standard of care.
- iv. Subsequent follow-up will be determined by pathology results:
 1. If biopsies show LGIN or less: next follow-up endoscopy will occur in a year.
 2. If any biopsies are found to have MGIN or HGIN, endoscopy with RFA will be repeated at 3 month intervals until resolution of MGIN or HGIN is demonstrated. If patient still harbors MGIN or HGIN after a maximum of 4 consecutive 3-monthly RFA sessions, escape treatment will be performed.
 3. If ESCC is found in any biopsy, the patient will be treated with escape treatment.

Outside the TA:

- v. If no USLs, biopsies will not be necessary
- vi. If USLs are found outside the TA, each lesion should be biopsied and treated per investigator's discretion.

1. If any biopsies from outside the TA are found to be MGIN or worse, patient will be treated and followed-up at the discretion of the physician under hospital standard of care.

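### The four-session RFA limit in Protocol section 9.4.1 is worded as a whole-study cap and contradicts the follow-up treatment rules; it should be limited to the treatment phase (minor)

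*Protocol*

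**What the plan says.** Protocol section 9.4.1 (Treatment Phase, Scenario #2) sets the limit: "a maximum of four RFA sessions will be performed in total for each patient in this study". The next sentence gives the consequence: "If USLs with MGIN or worse in the TA persist after four sessions, the subject is considered a failure for the primary endpoint". The same section says of the 12-month visit: "No RFA is provided to any subject at the 12-month primary endpoint biopsy visit".

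The follow-up phase has its own rules:

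- **Section 9.1, Table 2.** The row that begins "Circumferential or focal RFA at 12" is marked at months 3, 6 and 9 and again at years 2 to 5. Footnote 3, on escape treatment for residual disease in follow-up, reads "If persistent after 4 additional RFA sessions".
- **Section 9.4.2, annual visits.** For the treatment area: "All flat USLs will be treated with RFA", with an exception for clearly reactive lesions.
- **Section 9.4.2, persistent MGIN or HGIN.** For a patient who still has disease "after a maximum of 4 consecutive 3-monthly RFA sessions, escape treatment will be performed". The synopsis and section 9.4.3 give the same limit.
- **Section 9.10.** Recurrent disease is to be treated with RFA first, and with escape treatment only if it persists.

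The follow-up limit applies to consecutive sessions. No total for the follow-up phase is stated.

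**The concern.** The scope words of the cap cover the whole study, whereas the follow-up rules assume that RFA remains available after month 12. A site that reads the cap as written cannot follow both.

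This sentence limits treatment, so the wording has consequences. Suppose a 12-month responder who has already had four sessions develops a recurrence. Giving RFA as sections 9.4.2 and 9.10 direct would exceed the cap and count on paper as a deviation. Sections 9.8 and 14.2 require prior written approval from the sponsor and the IRB/EC for deviations outside an emergency. Withholding RFA would instead send the patient early to escape treatment.

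Early escape treatment could affect two secondary endpoints in section 5.2.2. Endpoint 8 counts 12-month responders who sustain or regain complete response with repeat RFA, so early EMR or ESD could lower it. Endpoint 9 also counts EMR and ESD, so only non-endoscopic escape treatment could lower it, and that would lower endpoint 8 as well.

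**Working it through.** The check is a count of sessions; no power or precision formula is involved.

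**Step 1. Where four comes from.** Sections 9.4.1 and 9.1 schedule one primary RFA, repeat RFA if needed at months 3, 6 and 9, and none at month 12:

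1 + 3 + 0 = 4.

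The figure therefore reproduces as the treatment-phase maximum at scheduled visits. The sentence after the cap supports this, since it ties persistence after four sessions to the 12-month primary endpoint.

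**Step 2. Four as a whole-study total.** Every enrolled patient treated per protocol has at least the primary session. Sessions left under the literal cap are 4 − (sessions used). The total after one full follow-up course is (sessions used) + 4.

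| Sessions used in treatment phase | Left under literal cap | Total after one full follow-up course | Excess over 4 |
|---|---|---|---|
| 1 | 3 | 5 | 1 |
| 2 | 2 | 6 | 2 |
| 3 | 1 | 7 | 3 |
| 4 | 0 | 8 | 4 |

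In every row, the literal cap leaves fewer than the four sessions that sections 9.4.2 and 9.4.3 allow.

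**Step 3. A path with no 3-monthly course.** Take a patient who needed only the primary session and then has a non-reactive flat USL in the treatment area, with biopsies of LGIN or less, at each annual visit. Section 9.4.2 calls for RFA at years 2, 3, 4 and 5:

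1 + 4 = 5, which again exceeds 4.

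**Step 4. Weight of one patient in endpoint 8.** Section 13.2 expects a 12-month response of 80% to 90%. Assuming this gives 80 to 90 responders out of 100, one patient is worth:

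- 1/90 = 1.1 percentage points
- 1/80 = 1.25 percentage points

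**Step 5. How many patients.** The documents give neither the number of sessions used per responder nor recurrence by number of sessions, so no estimate is made.

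**The case against.** The best reply is that context already settles the scope. The sentence sits under the treatment-phase heading, within the month 3, 6 and 9 visits, and is followed at once by a rule about the primary endpoint. Follow-up has its own section, and its limit appears consistently in four places. Section 7.6 plans up to 8 catheters per patient across both phases and lets that number be exceeded for disease found in follow-up, so treatment after month 12 was clearly foreseen. An investigator working from section 9.4.2 would probably just follow it.

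The harm also needs a chain of events: a responder with too few sessions left, a recurrence, and a site that puts the cap above section 9.4.2. In the earlier cohort described in section 6.2, recurrence was 9% (7/78). That figure comes from mixed regimens and does not bound this trial, but it suggests that full follow-up courses would be uncommon. Figures 1 and 2 were not available for this check and may show the limits by phase.

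Most of this stands as evidence of intent, and it is why the point is minor. It does not correct the sentence, whose scope words explicitly cover the study and not the phase. The context is also less clean than it looks. Section 9.4.1 uses the term follow-up for its own month 3, 6 and 9 visits. Section 9.4.2 sends follow-up investigators back to the scenario that holds the cap: "each lesion will be biopsied (as described in section 9.4.1, scenario #2". That reference concerns biopsy method only and does not import the cap, but it puts the sentence in front of the reader at the wrong moment.

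**Conclusion.** The concern holds, as a minor error. The cap is correct for the treatment phase and wrong for the whole study. One full follow-up course leads to 5 to 8 sessions in all, against the 4 that the sentence allows.

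These totals assume that the follow-up limit applies afresh to each run of consecutive sessions. That is an interpretation, since the protocol says only that the sessions are consecutive. The contradiction does not depend on it, because a single follow-up course is enough to break the cap.

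The possible effects on endpoints 8 and 9 arise only if a site applies the cap literally. They are likely to be small, but their size cannot be derived from the documents. The value of 1.1 to 1.25 points per patient for endpoint 8 rests on the assumed 80 to 90 responders. The primary endpoint, the sample size and the SAP are not affected.

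**What to change.** In section 9.4.1, Scenario #2, replace the scope words so that the sentence limits each patient to four RFA sessions in total *during the treatment phase*. Do not add a list of visits: under Scenario #3 and section 9.4.3, RFA after escape treatment is timed from that treatment and can fall between scheduled visits. Leave the follow-up limit in section 9.4.2 as it is. Check that Figures 1 and 2 agree with both limits.

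The cost is one phrase in the protocol and a check of two figures. The SAP needs no change.

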- Central pathology review of biopsies for all biopsies or resection specimens during FU, with independent reading from two pathologists in case of recurrent or progressive disease.
 - Safety assessment

If clinically indicated, Investigator may always perform extra endoscopies in addition to figure 2.

9.4.3. Escape treatment: Endoscopic (EMR or ESD) or Non-Endoscopic Therapy during Treatment or Follow-up Phase

Several indications for escape treatment exist:

[figure not shown]
- Any non-flat lesion (Paris type 0-I, 0-IIa, 0-IIc, 0-III) during treatment or follow-up phase
- Any abnormality under WLE or Lugol's chromoendoscopy that is suspicious for ESCC (e.g. 'pink sign' USL, defined as a color change after Lugol's staining: initially whitish yellow and pink 2-3 minutes later)
- ESCC in biopsies during treatment or follow-up phase (defined as progression of disease)
- Presence of MGIN or worse in any biopsies from TA at the 12 months endoscopy
- Persistent MGIN or worse during follow-up phase despite a maximum of 4 consecutive 3-monthly RFA sessions
- If clinically indicated per Investigator's discretion

Escape treatment can be performed endoscopically (EMR or ESD), or non-endoscopically (surgery, radiotherapy or chemotherapy) per investigator's discretion under the hospital's standards of care. All patients, regardless of treatment used or failure of the primary endpoint, will be followed to study termination for assessment of secondary endpoints:

- Patients who undergo non-endoscopic therapy will be considered a failure for the primary endpoint, but will be tracked through the 5-year follow-up to assess secondary endpoints.
- For patients who undergo endoscopic treatment, final pathology is required:
 - If the disease stage is eligible for endoscopic escape treatment (i.e.: good to moderate differentiation and negative vertical resection margins and m1/m2/m3/sm1 disease and without lymphovascular infiltration), further treatment and/or follow-up endoscopies after the escape treatment will occur according to

Medtronic Confidential

- the study protocol. The application of RFA after endoscopic resection may be performed after minimally 8 weeks later.

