- If the disease stage exceeds the limits for endoscopic treatment (i.e.: either one of: poor differentiation, positive vertical resection margins, sm-2 or sm-3 invasion or lymphovascular invasion), patient will be considered a failure for the primary endpoint. The Investigator will decide which escape treatment to perform, and the patient will be followed to study termination for assessment of secondary endpoints.
 - If histology does not demonstrate ESCC, patient will remain eligible for inclusion as a success in the primary and secondary endpoints. The application of RFA after endoscopic resection may be performed after minimally 8 weeks later.

Discharge Instructions after RFA Procedures

- Liquid acetaminophen with narcotic per oral as needed for pain
- Liquid antacid, lidocaine, and sucralfate slurry or Almagate Suspension for first 5 days, as needed
- Liquid diet for 3 days, then soft diet for 4 days, then normalize
- At the direction of the physician, anti-thrombotic agents should be avoided for 7 days before and after any RFA procedure.
- All patients commence proton pump inhibitor (PPI) medication (esomeprazole 40 mg bid) after the Primary RFA to allow restoration of a normal epithelium. Patients will continue PPI after each RFA session until endoscopy and biopsy demonstrate no further MGIN+ and no need for further RFA.
- Contact physician for any vomiting, shortness of breath, pain not controlled on medication, fever, or bleeding.
- Subject is educated to not eat very hot foods including soups, and not drink very hot liquids as such behavior can delay healing and potentially promote stricture formation and prolonged pain. Subject is instructed to not eat or drink anything in which they are unable to comfortably place their finger for at least 10 seconds prior to ingesting.

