9.10. Definitions

-CR = complete response

Absence of MGIN or worse in biopsies from TA at a single endoscopy.

- Escape treatment

Escape treatment is indicated for lesions with (i) ESCC in biopsies, (ii) non-flat lesions, or (iii) lesions otherwise suspicious for ESCC (e.g. pink-sign positive lesions). Escape treatment will be performed by investigator's distinction and per hospital's standards of care. Subsequent pathology assessment determines whether patient is defined as progressor and failure for the efficacy endpoint.

- Progressive disease

This term is applicable during the whole study. Progressive disease is defined as ESCC in any biopsy or resection specimen. Progressive disease on biopsy will always be treated with escape treatment.

Patients with progressive disease within the first 12 months are a failure for the primary efficacy endpoint, whereas progression patients in subsequent 4 years of follow-up are a failure for the durability endpoint. Progressive disease can be classified into 2 categories based on pathology:

- Eligible for endoscopic treatment, if all of the following characteristics are met: good to moderate differentiation, negative vertical resection margins, m1/m2/m3/sm1 disease and without lymphovascular infiltration.
- Exceeding the limits for endoscopic treatment, if any of the following characteristics was found: poor differentiation, positive vertical resection margins, sm-2 or sm-3 invasion or lymphovascular invasion.

- Treatment failure

This term is applicable to the first 12 months of study. All patients with residual ESCN at the 12 months endoscopy, and patients who progressed to ESCC before 12 months, will be defined as treatment failures.

- Sustained CR

This term is applicable during follow-up, to all patients that were not defined as treatment failures at 12 months. Sustained CR is defined as sustained eradication of MGIN or worse in biopsies from TA, during all FU endoscopies until 60 months.

- Recurrent disease

This term is applicable during follow-up, to all patients that were not defined as treatment failures at 12 months. Recurrent disease is defined as flat (Paris type 0-IIb) USLs with MGIN or HGIN in biopsies from TA during FU, independent of baseline pathology. Recurrent disease will be treated with RFA initially, or escape treatment if persistent, as described in section 9.4.3

10. Risks and Benefits

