7.9.1. Primary Endpoint

The primary endpoint is the percentage of subjects with "complete response (CR)", defined as complete eradication of squamous histological abnormalities (MGIN or worse) within the treatment area (TA) at 12 months after the initial treatment session (per-protocol analysis). Patients who show ESCC in biopsies or resection samples are defined as failures for this endpoint, even if subsequent biopsies at 12 months indicate CR.

The primary study hypothesis is that 80% of treated subjects will have a complete response.

Patients

All 100 patients that are included in the cohort will be assessed for the primary endpoint. The run-in patients will not be included for the primary endpoint analyses.

Biopsies

Only biopsies obtained from the original USL bearing portion of the esophagus (the treatment area) will be used in the analysis for the primary endpoint at 12 months. At 12 months, MGIN or worse noted in any biopsy from outside this region are not considered failures of ablation for the purposes of the primary endpoint.

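### Conflicting primary-endpoint rules for a cohort subject given non-endoscopic escape therapy before month 12 without ESCC on histology

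*Protocol*

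**What the plan says.** Protocol 9.4.1, Scenario #3, covers non-flat lesions and lesions suspicious for ESCC in the treatment area before month 12. It sends these subjects to escape treatment and allows this without a confirming biopsy: "the Investigator can perform escape treatment if deemed necessary, regardless of the biopsy result". It then gives its own endpoint rule: "The patient will be considered a failure for the primary efficacy endpoint only if escape treatment histology shows progression to ESCC". Without ESCC, "the patient will return in 3 months from escape treatment for possible RFA and will be eligible for success in the primary endpoint".

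Protocol 9.4.3 defines escape treatment by type: "Escape treatment can be performed endoscopically (EMR or ESD), or non-endoscopically (surgery, radiotherapy or chemotherapy) per investigator's discretion". Its endpoint rule for the second type is "Patients who undergo non-endoscopic therapy will be considered a failure for the primary endpoint", with no reference to histology. It has a separate no-ESCC rule, listed among the points for patients treated endoscopically: "If histology does not demonstrate ESCC, patient will remain eligible for inclusion as a success in the primary and secondary endpoints".

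Protocol 9.10 leaves the outcome after escape treatment to pathology and defines treatment failure by disease status alone: "All patients with residual ESCN at the 12 months endoscopy, and patients who progressed to ESCC before 12 months, will be defined as treatment failures".

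SAP 7.9.1 has one override: "Patients who show ESCC in biopsies or resection samples are defined as failures for this endpoint, even if subsequent biopsies at 12 months indicate CR". Protocol 5.2.1 has the same one. Neither mentions non-endoscopic therapy.

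SAP 7.1.3 and Protocol 13.3 make the primary analysis per protocol and require a valid study outcome. Protocol 5.2.1 and SAP 7.9.1 also say that all 100 cohort patients will be assessed for the primary endpoint.

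**The concern.** An unconditional failure rule and a failure rule limited by 'only if' cannot both hold for a subject who has surgery, radiotherapy or chemotherapy and no ESCC on histology. The protocol permits such a subject. Escape treatment may proceed whatever the biopsy shows, its type is left to the investigator, and 9.4.3 also lists a general clinical indication at the investigator's discretion.

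The primary endpoint is meant to describe eradication by a course of RFA. If the 9.4.3 rule is not applied, a treatment area cleared by radiotherapy or chemotherapy could enter the numerator. Any departure from 9.4.3, whether to success or to exclusion, raises the reported rate. The study is single-arm and unblinded, so the choice between rules should not be left until the cases are known. A programmer working from SAP 7.9.1 alone would not see the 9.4.3 rule.

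**Working it through.** **Step 1: the plan's own precision figure.** The inputs are N = 100 and an expected complete response (CR) rate of 80% to 90% (Protocol 13.2, SAP section 6), with a two-sided 95% interval. The Wald half-width is 1.96 × √(p(1 − p)/N).

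- p = 0.80: 1.96 × √(0.16/100) = 1.96 × 0.040 = 7.8 points
- p = 0.90: 1.96 × √(0.09/100) = 1.96 × 0.030 = 5.9 points

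This reproduces the stated 6% to 8%. Exact Clopper-Pearson half-widths are 8.3 and 6.4 points.

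**Step 2: one subject under each rule.** Take a cohort subject with non-endoscopic escape therapy before month 12 and no ESCC in any specimen.

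| Place | Rule | Outcome |
|---|---|---|
| Protocol 9.4.3 | Non-endoscopic therapy is a failure | Failure |
| Protocol 9.4.1, Scenario #3 | Failure only with ESCC on escape-treatment histology | Not a failure; may still succeed |
| Protocol 9.10 | Residual ESCN at 12 months, or ESCC before it | Failure only if 12-month biopsies are positive |
| Protocol 5.2.1, SAP 7.9.1 | CR from 12-month biopsies, with ESCC as override | CR if biopsies are clear |
| SAP 7.1.3, Protocol 13.3 | Valid outcome required | Possibly excluded if there is no biopsy |

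Eligibility for success is not success: the 12-month biopsies must still be clear. The last row is a possibility only, because validity is not defined as having a 12-month biopsy.

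**Step 3: does the cross-reference settle it?** Scenario #3 refers to 9.4.3 twice, once for the description of escape treatment and once for continuation on the trial. The endpoint sentence stands between the two and refers to neither. The no-ESCC rule in 9.4.3 belongs to the endoscopic branch, so it does not cover this subject.

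**Step 4: size.** Let k be the number of such subjects. The documents give no rate, so k is an assumption. With 80 other responders and N = 100, the CR rate is 80/100 if they count as failures, (80 + k)/100 if as successes, and 80/(100 − k) if excluded. Wald 95% intervals are in brackets.

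| k | Failure | Success | Excluded |
|---|---|---|---|
| 1 | 80.0% (72.2–87.8) | 81.0% (73.3–88.7) | 80/99 = 80.8% (73.1–88.6) |
| 3 | 80.0% (72.2–87.8) | 83.0% (75.6–90.4) | 80/97 = 82.5% (74.9–90.0) |
| 5 | 80.0% (72.2–87.8) | 85.0% (78.0–92.0) | 80/95 = 84.2% (76.9–91.5) |

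Each subject moves the estimate by 1 point if counted as a success and by about 0.8 points if excluded. Up to k = 5 the shift is at most 5 points, less than the half-width of 7.8 points at 80%.

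**The case against.** The best reply is that the protocol already has a specific rule and Scenario #3 points to its section. Section 9.4.3 is devoted to escape treatment and splits it by type: failure for non-endoscopic therapy, histology for endoscopic. Scenario #3 assumes a histology result from the escape treatment and a return for possible RFA, which fits EMR or ESD better than surgery, radiotherapy or chemotherapy. Read together, the specific rule would govern and the Scenario #3 sentence would be loose drafting. This is probably what the authors meant. But Scenario #3 does not say so, and the rule is absent from the endpoint definition, 9.10 and the SAP.

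Four further points limit the concern.

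- A reader might infer that the SAP definitely counts these subjects as responders. It does not say that. It states the ESCC override and is silent on other protocol failure rules. It was also written for protocol version 4, while the protocol reviewed here is version 7.0.
- A reader might infer that a subject without an evaluable treatment area drops out of the per-protocol set. That is one possible reading, and the statements that all 100 cohort patients will be assessed weigh against it.
- Crediting another treatment's effect to RFA is not in itself a departure from the plan. The plan openly allows success after EMR or ESD when no ESCC is found. The point therefore rests on the conflict between rules.
- Protocol 13.6 plans a subgroup analysis by use of escape treatment, which would help to show such cases. SAP 7.11 leaves that factor out.

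**Conclusion.** The conflict is in the text and concerns the primary endpoint: for this type of subject, 9.4.3 and Scenario #3 give incompatible answers, and the endpoint definitions and SAP do not settle the matter. The likely effect is small, about one percentage point per subject against a half-width of 6 to 8 points, and the endpoint is summarised descriptively with a confidence interval. That size rests on an assumed count, since the documents give no frequency and non-endoscopic therapy without ESCC should be rare.

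A reader might look for a frequency in the long-term results reported in Protocol 6.2, where 5 of 12 subjects with residual disease had non-endoscopic treatment. Those subjects already had residual ESCN and were treated for later progression, so they say nothing about this case. Nor do the documents support a claim that the primary result is materially biased. What they support is that the classification should be fixed in writing before analysis, because both departures from 9.4.3 favour the device.

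**What to change.** Reconcile the sections by carrying the classification already in 9.4.3 into Protocol 5.2.1, the treatment-failure definition in 9.10, and SAP 7.9.1. Suggested wording: a cohort subject who receives surgery, radiotherapy or chemotherapy as escape treatment before the 12-month endpoint biopsy is a non-responder, whatever the histology, and stays in the primary-analysis denominator. The time limit should be explicit, because 9.4.3 covers the follow-up phase as well. In Scenario #3, limit the 'only if' sentence to endoscopic escape treatment.

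This changes how an outcome is classified and not which treatment any subject receives. It costs one sentence in the SAP and matching wording in the protocol, with no new data. The downside is a CR rate that may be slightly lower than under the other readings.
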